**PROTOCOL TITLE**

Effects of Anorexia Nervosa on Peak Bone Mass

**FUNDING**

NIH, and Global Foundation for Eating Disorders

**VERSION DATE**

March 29, 2018

**SPECIFIC AIMS**

Concisely state the objectives of the study and the hypothesis being tested.

One of the goals of this proposal is to investigate if co-administration of rhIGF-1 with physiologic estradiol replacement to adolescent girls with AN will increase BMD more than estrogen monotherapy, and bone mass will approach that seen in healthy adolescent girls.

An additional aim for the prospective study is to determine whether co-administration of rhIGF-1 with estradiol to mimic the normal pubertal milieu:

- A) Stimulates bone formation through an IGF-1 mediated anabolic effect
- B) Increases bone density to a greater extent than estrogen monotherapy
- C) Improves bone mass accrual to approach that in healthy controls

Further more we will investigate if co-administration of rhIGF-1 with physiological estradiol replacement will improve bone microarchitecture and bone strength in girls with AN. In a cross-sectional study of adolescent girls with AN and healthy adolescent girls, we will determine whether:

- A) Cortical and trabecular bone density and microarchitecture at the ultradistal radius (non-weight bearing bone) and tibia (weight bearing bone) as assessed by HR-pQCT, and bone strength, as assessed by finite element analysis (FEA), are abnormal in AN compared to controls, and are associated positively with nutritional and hormonal predictors of bone mass, including BMI, body fat, fat-free mass, estradiol and IGF-1 levels

In a prospective study of adolescent girls with AN we will determine whether:

- B) Co-administration of rhIGF-1 with transdermal estrogen improves cortical and trabecular bone microarchitectural parameters (assessed by HRpQCT) and bone strength (assessed by FEA) more than estrogen alone to approach that in normal adolescent girls. Girls with AN receiving estradiol alone will have an increase in bone microarchitecture and strength versus baseline, but will not normalize compared to healthy controls
- C) Changes in IGF-1 levels are associated positively with changes in measures of bone density, microarchitecture and strength.

## BACKGROUND AND SIGNIFICANCE

Provide a brief paragraph summarizing prior experience important for understanding the proposed study and procedures.

Anorexia nervosa (AN) is the third most common chronic illness among adolescent girls (1), with a prevalence of 0.2-1.0% in Western societies (2, 3). The prevalence rate of AN is 269.9 per 100,000 for females, with a linear increase in incidence reported for the 15-24 year age group over the last 50 years (1). Primarily psychiatric in origin, AN results in numerous medical complications, which lead to increased morbidity and mortality in this young population. Although the endocrine and metabolic disturbances of AN typically resolve with weight gain, low bone mineral density (BMD) is a frequent and persistent co-morbid complication of AN. *There are no effective approved therapies to normalize bone mass accrual in this population.*

Why is the low bone mass characteristic of AN of critical health importance? (i) The prevalence, rapidity of development, and severity of low bone mass in adolescents and young women with AN have associated morbidity, (ii) low BMD acquired during adolescence may impose life-long increased fracture risk, (iii) despite the increased prevalence of this disorder, treatment strategies in this population do not exist, and (iv) AN represents a unique model in which to investigate the profound consequence of nutritional deprivation and pubertal disruption on bone mass acquisition. The majority of adolescent girls with AN have low BMD of early onset involving both trabecular and cortical bone (4-6), and clinical fractures occur even in this young age group; lumbar BMD is reduced  $>2$  SD in adolescent AN girls, often after only one year of illness (5). A study in 170 adolescents 10-17 years old with AN found that 44% of girls with  $\geq$  six months of amenorrhea had low lumbar spine bone mass (7). Unfortunately, the time to recovery in adolescents with AN is long (8), and therefore, severe bone mass deficits are common. We have shown that adolescents with AN have a marked reduction in bone mass compared to bone age-matched controls using height-adjusted BMD calculations to eliminate potential bone size confounders (9). A population-based long-term fracture risk cohort study from the Mayo Clinic found that the cumulative incidence of any fracture 40 years after the diagnosis of AN is 57% (10). Low bone density in AN is a consequence of several hormonal alterations including hypogonadism, low IGF-1 levels, high levels of cortisol and alterations in certain hormones such as ghrelin, leptin and PYY that are altered in conditions of low energy availability.

Why is this young population at such high risk for severe and permanent osteopenia and skeletal fragility? The onset of AN most frequently occurs during adolescence, a period of maximal bone accretion, with  $> 90\%$  of bone mass accrued by 18 years of age (11). Because adolescence is a critical time for attainment of peak skeletal mass, reduction of BMD during this crucial period may lead to long-term morbidity. Indeed, we found that in contrast to normal adolescents who demonstrate marked bone accretion during puberty, adolescents with AN do not increase their bone mass (12). Therefore, bone mass remains low in these girls during a critical period in normal bone development. We have previously shown that adults with onset of AN during adolescence have lower spine BMD than those with adult-onset AN, despite comparable years of amenorrhea (13). Furthermore, low bone mass in adolescents with AN may be permanent despite recovery (14). Approximately half of young women with AN have persistent osteopenia, even after  $>10$  years (15-17). Therefore, there may be a narrow “window-in-time” during adolescence in which maximal accrual of bone mass occurs and during which treatment paradigms to maximize bone accrual must be implemented.

The overall significance of this problem: A large number of adolescent girls suffer from anorexia nervosa resulting in major deficits in bone mass and increased skeletal fragility, which may be permanent. Our proposed study will 1) test the efficacy of replacing a deficiency of an

endogenous bone anabolic hormone, IGF-1, with estradiol as a unique therapy for the low bone formation state in adolescents with AN and 2) enable an understanding of the effects of this disease and its treatment by measuring not only compartment-specific changes in bone density, but microarchitecture and strength at weight bearing and non-weight bearing sites.

Given the increasing prevalence of AN, its profound consequences on bone health, and lack of optimal treatment interventions, these studies will provide critical data needed to identify optimal treatment strategies for this severe co-morbid disease using state- of- the- art endpoints of BMD, bone microarchitecture and strength. Although both low IGF-1 and hypogonadism are associated with increased skeletal fragility in AN, the mechanisms by which these factors interact are incompletely understood. Specifically, the increased skeletal fragility that is associated with AN is poorly reflected by DXA-derived BMD. Furthermore, the magnitude and mechanisms by which IGF-1 deficiency and hypogonadism influence bone microarchitecture are not defined. The growing incidence of eating disorders in adolescent girls and their long-term effects on skeletal health provide strong rationale for studies that will provide a better understanding of these issues and the evaluation of rational therapeutic approaches. The studies described in this proposal utilize both cross-sectional and RCT approaches to achieve this goal. Additionally, our utilization of sophisticated techniques such as high resolution peripheral QCT (HR-pQCT) (described below) will improve our understanding of the relationship between IGF-1, gonadal steroids and bone quality and will aid in the development of effective therapies in the treatment of skeletal fragility in AN.

Furthermore, in recent years, there has been an increasing awareness of the bone fat connection. In the marrow, osteocytes and adipocytes arise from a common progenitor. Recent studies have shown an increase in bone marrow fat in adults with anorexia nervosa which is also correlated inversely with bone mineral density. We will assess the effect of estrogen (bone anti resorptive hormone) and IGF-1 (bone anabolic hormone) on marrow fat in girls with AN and in comparison with healthy controls who receive no intervention. Also bone marrow fat and preadipocyte factor, Pref-1, decrease after recovery from anorexia nervosa. We will determine associations of changes in bone mass following therapy with changes in marrow fat and Pref-1 levels over the same duration. This will help us delineate the physiological connection between bone marrow fat and bone mineral density and structure in AN.

## RESEARCH DESIGN AND METHODS

Briefly describe study design and anticipated enrollment, i.e., number of subjects to be enrolled by researchers study-wide and by Partners researchers. Provide a brief summary of the eligibility criteria (for example, age range, gender, medical condition). Include any local site restrictions, for example, "Enrollment at Partners will be limited to adults although the sponsor's protocol is open to both children and adults."

Over the proposed 5 year grant, 100 girls with AN and 36 healthy controls will be enrolled at MGH. We will screen up to 272 subjects. Subjects with AN will be randomly assigned by the MGH Research Pharmacy to one of two arms: (i) IGF-1 with estrogen or (ii) estrogen alone with placebo for 12 months. Healthy controls will be followed prospectively for 12 months. Control subjects will complete the screen and baseline visit only. Study staff will follow-up with control subjects via a telephone call at 12 months after their baseline visit. This telephone call will serve to inform study staff of any medical changes or major life events that have occurred since the baseline study visit. We anticipate a 20% dropout rate based on our previous studies. Only AN subjects will take calcium and vitamin D supplement pills daily; dosage of vitamin D will be based upon each subject's serum levels.

AN Subjects: Subjects with AN will be 14-22 years old- an age span before peak bone mass is achieved, with a bone age (BA) of  $\geq 14$  years and meet DSM V criteria for AN. Our inclusion criteria for AN refers to the diagnosis of (a) Anorexia Nervosa or (b) Atypical Anorexia Nervosa with significant weight loss per DSM V. We will use a BA of 14 years as the cut-off because all epiphyses are near fusion and 98% of adult height has been attained at this skeletal age (19).

Control Subjects: (i) Healthy adolescent girls 14-22 years with a BA of  $\geq 14$  years; (ii) BMI between the 10th-90th percentiles for age, (iii) regular menstrual periods every 28-35 days and/or  $>9$  menses within the last 12 months for subjects  $\geq 2$  years post-menarche. Control subjects will be studied during the early follicular phase of their cycles (days 1-10).

Inclusion Criteria: AN:

- Subjects with AN will be 14-22 years old
- Bone age (BA) of  $\geq 14$  years
- Meet DSM V criteria for AN or Atypical AN with significant weight loss
- Subjects at MGH will be evaluated by an MGH study psychiatrist or psychologist before enrollment.

Inclusion Criteria: Controls:

- Healthy adolescent girls 14-22 years
- BA of  $\geq 14$  years
- BMI between the 10th-90th percentiles for age
- Regular menstrual periods every 28-35 days and/or  $>9$  menses within the last 12 months for subjects  $\geq 2$  years post-menarche.

Exclusion Criteria:

- Diseases known to affect bone metabolism including untreated thyroid disease, Cushing's syndrome, diabetes, pituitary disease, renal failure and prior bone fracture within six months of the study.
- Medications known to affect bone metabolism, including gonadal steroids and excluding oral contraceptives or estrogen/progestin containing compounds within two months.
- Evidence of suicidality, psychosis, or substance abuse based on an interview with the study psychiatrist or psychologist and recommendations.
  - In the event that evidence of suicidality, psychosis or substance abuse is uncovered in the interview, the current treatment team for the subject will be contacted and informed by the current study psychologist or psychiatrist. In the event a subject does not have a treatment team in place, referrals will be made by the current study psychologist or psychiatrist. If danger is imminent and safety can not be guaranteed, 911 can be called.
- Premature ovarian failure, as demonstrated by an elevated FSH.
- Abnormal TSH.
- Hematocrit  $<30\%$ , Potassium  $<3.0$  mmol/L, Glucose  $<50$  mg/dl
- Pregnancy
- History of malignancy
- Absolute contraindications to estrogen therapy (for girls with AN)

Briefly describe study procedures. Include any local site restrictions, for example, "Subjects enrolled at Partners will not participate in the pharmacokinetic portion of the study." Describe study endpoints.

Screening Visit: Eligibility for participation in the protocol will be determined at a screening visit. Evaluations on this visit will include:

- (a) History and physical exam including Tanner stage, height and weight.
- (b) Blood laboratory tests for glucose, TSH, LH, FSH, potassium and hematocrit, IGF-1, urine or serum pregnancy test and Bone age estimated using an x-ray of the left hand and wrist by standards of Greulich and Pyle (19).
  - i. In cases where the family can provide records of the lab work required for screening performed within two months of the screening visit, we will not repeat those labs.
  - ii. Blood laboratory tests can be done at baseline visit if unable to obtain at screening visit. If blood laboratory tests are done at baseline, medications will be withheld until laboratory results are received and assessed.

Baseline Visit:

- (a) Bone age estimated using an x-ray of the left hand and wrist by standards of Greulich and Pyle (19) if not completed at the screening visit.
- (b) Complete History and Physical: Including growth, menstrual history, Tanner staging staging and fundoscopic exam.
- (c) Anthropometric Measurements: Height will be measured in triplicate using a stadiometer, and weight on a single electronic scale in the Clinical Research Center (CRC).
- (d) Nutritional Assessment: CRC dieticians at MGH will evaluate nutritional status using 4-day food records for macro- and micronutrient intake (Nutrition Data Systems, version 4, Minneapolis, MN) and indirect calorimetry (metabolic cart) to determine respiratory quotient (RQ) and resting energy expenditure. (All subjects consent to the metabolic cart, although it is treated as optional during the study. A food diary log may be provided at the screening visit or baseline visit. Although all subjects consent to the food diary log, its completion is treated as optional during the study.)
- (e) EDI2: Eating Disorders Inventory-2 questionnaire, which has been validated in adolescent patients with eating disorders (25) and includes assessment of body image. This is a 91-item, 11 scale, six-point forced-choice self-report inventory assessing behavioral and psychological traits common in AN. (This can be completed at the screen visit)
- (f) BDI-II: Beck Depression Inventory-2 questionnaire is a self-report inventory assessing depression and mood traits common in AN (All subjects consent to standardized psychiatric tests, although they are treated as optional during the study. This component can also be completed at the screen visit, instead of the baseline visit.). For safety concerns related to suicidality, after every administration of the BDI-II, a research assistant or study nurse will review the suicidality item of each measure. If any subject scores a “2” or “3” on the BDI-II “Suicidal Thoughts or Wishes” item, or if the total score corresponds to “moderate” or “severe” depression (see below), the study psychologist/psychiatrist will be paged for further assessment with the participant. BDI-II scoring ranges are as follows:
  - a. 0-13: minimal depression
  - b. 14-19: mild depression
  - c. 20-28: moderate depression
  - d. 29-63: severe depression
- (g) STAI: State Trait Anxiety Inventory questionnaire is a 40-item and four-point Likert scale self-report inventory assessing state and trait anxieties common in AN. (All subjects consent to standardized psychiatric tests, although they are treated as optional during the study. This component can also be completed at the screen visit, instead of the baseline visit.)

- (h) Activity Assessment: Habitual exercise and activity will be assessed using a standardized exercise questionnaire, which provides a good estimate of past year physical activity in adolescents (26, 27). (All subjects consent to the activity assessment, although it is treated as optional during the study.)
- (i) Bone Turnover Markers: Serum for PINP and C-telopeptide (CTX).
- (j) Calcium Metabolism: Blood for calcium, phosphorus, 25(OH) D, 1,25(OH)2D, PTH.
- (k) Hormonal Evaluation: Serum for IGF-1, IGFBP-3, SHBG, estradiol, leptin.
- (l) If not obtained at screening visit: Blood laboratory work for glucose, TSH, LH, FSH, potassium and hematocrit, and IGF-1. Medications will be withheld until laboratory results are received and assessed.
- (m) Bone Mass Density: lumbar spine (AP and lateral), hip, radius, whole body areal BMD, BMC and BA will be measured by dual energy x-ray absorptiometry (DXA: Hologic QDR 4500, Waltham, MA).
- (n) Body Composition: Whole body DXA will be performed to assess fat and lean mass.
- (o) Bone morphology, microarchitecture and strength will be determined at the ultradistal radius and distal tibia using HR-pQCT (Xtreme CT, Scanco Medical AG). Bone strength will be determined using FEA of HR-pQCT scan data (28).
- (p) Safety Evaluation: Urine or Serum HCG (to rule out pregnancy) and fasting glucose.
- (q) Thigh and abdomen MRI and an L4 MR spectroscopy will be performed to assess bone marrow fat. We will also add Pref-1 assessment to the already collected blood. This will only be repeated at 12 months for patients with anorexia nervosa.
  - a. This study is optional for AN subjects and non-optional for HC subjects
- (r) Study Drug Reminders: We will set up medication reminders on phone calendars for those who consent to the optional reminders. Subjects may decrease or turn off reminders at any time. All patient information will remain confidential, and no identifiers will be used. Additionally, all subjects will receive paper medication calendars to keep track of each dose taken and to return to study staff at each visit.
- (s) Two subtests, Vocabulary and Matrix Reasoning, from the Weschler Abbreviated Scale of Intelligence (WASI), a Color-Word Interference Test subtest from the Delis Kaplan Executive Functioning Scale (DKEFS), and the California Verbal Learning Test (CVLT). (All subjects consent to the cognitive assessments, with the intention that they will be completed to the extent that time, subject schedule, and circumstances allow during the study visit.)

All blood samples will be drawn fasting or at least two hours after food. Subjects who are unable to fast overnight will have the option to complete the metabolic test while fasting for two hours.

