Specific Aim 1B. We will analyze the impact of rhIGF-1 with estrogen (n=50) versus estrogen alone (n=50) on levels of the bone turnover markers, PINP and CTX, in girls with AN at 3, 6, 9 and 12 months using a repeated measures ANOVA. The primary planned analysis will be the difference in mean levels by treatment group during the 3, 6, 9 and 12 month observations. As for Specific Aim 1A, we will examine whether effects of combination therapy persist following discontinuation of therapy by examining these markers after 12 months of stopping therapy.

Specific Aim 1C. We will use the longitudinal model described above to compare the rate of bone mass accrual in girls with AN who receive rhIGF-1 with estrogen (n=50) with that seen in healthy controls (n=36). We expect the change in BMD in AN girls to exceed that in controls because of a “catch up” effect when rhIGF-1 is used with estradiol. We will control for multiple comparisons in our analysis when comparing against controls. Both unadjusted and multiplicity adjusted analyses will be presented.

Specific Aim 2A. In a cross-sectional design, we will compare the described HR-pQCT endpoints and bone strength (as assessed by FEA) in girls with AN (n=100) to those in healthy adolescents (n=36). We will use the Student t test when variables are normally distributed or when transformations can be performed to approximate a normal distribution; otherwise, we will use non-parametric tests such as the Wilcoxon rank sum test. Our preliminary data indicate lower trabecular bone density in 8 girls with AN compared with 6 controls (162 ± 27 vs. 209 ± 36 g/cm³, $p=0.02$). Based on these data, with 100 girls with AN and 36 controls in the study, we have >99% power for detecting a significant difference in trabecular bone density between the groups at an alpha level of 0.05. Another component of this specific aim is to determine the extent to which DXA parameters and possibly clinical parameters predict bone microarchitecture in the 100 adolescents with AN. This will help elucidate the role of DXA in the future clinical evaluation of adolescents with AN. Linear regression followed by regression modeling will be performed to determine hormonal, body composition, nutritional and exercise predictors of bone microarchitecture and bone strength in girls with AN and healthy adolescent girls.

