Specific Aim 2B. The goal of this specific aim is to determine prospectively changes in bone microarchitecture and bone strength in girls with AN who receive rhIGF-1 and estrogen therapy (n=50) compared with changes in AN receiving estrogen alone (n=50). Bone microarchitecture will be assessed using HR-pQCT and bone strength using FEA at baseline, six, 12 and 24 months of the study. Our second primary study endpoint is the change in trabecular bone density in the two treatment groups over the course of the study. With 100 subjects (50 in each group) we will have an 80% chance of detecting a significant difference ($p=0.05$ two sided) in change in trabecular bone density in girls with AN who receive rhIGF-1 and estrogen compared with estrogen alone if the true relative change is 3.5% over the 12 month period. This assumes a standard deviation of relative change of 6%, as was found in the group of AN women who gained weight in a study by Milos *et al* (39). To understand the clinical meaning of such a change we note that AN women had a 20% decrease in trabecular bone density compared to normal women. The analysis will be accomplished using a longitudinal mixed model ANOVA with a random patient and time (slope) effect. The measure of interest will be the group time interaction. We estimate a 20% dropout rate based on our previous study. A secondary analysis will be a joint model with weight gain as described for Specific Aim 1. We will also compare changes in total cross-sectional area, cortical thickness, TbN, TbTh and TbSp between AN receiving rhIGF-1 and estrogen with AN receiving estrogen alone. Although this is not a specific aim, it will be interesting to compare the changes in BMD with the change in bone strength. An issue is that BMD and bone strength are measured in different units. In order to make the comparisons understandable, we will transform both to percent predicted using the data from healthy adolescent girls. Then we will fit a joint model for both measurements to assess the relationship between the two and which measure is affected most by treatment. In addition, we will examine these endpoints 12 months after stopping therapy to determine whether effects persist after discontinuing combination therapy. When comparing with healthy adolescent girls, we will adjust for multiple comparisons. Both unadjusted and multiplicity adjusted analyses will be presented.

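### Healthy controls are scanned once, so the Aim 1C comparison of their BMD accrual rate with that of treated AN girls cannot be estimated

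*Protocol*

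**What the plan says.** Under Specific Aim 1C the SAP takes the random-effects model from Aim 1A and will "compare the rate of bone mass accrual in girls with AN who receive rhIGF-1 with estrogen (n=50) with that seen in healthy controls (n=36"). It adds a directional expectation: "We expect the change in BMD in AN girls to exceed that in controls". It also promises that "We will control for multiple comparisons in our analysis when comparing against controls". The matching protocol aim (Specific Aims, item C of the prospective study) reads "Improves bone mass accrual to approach that in healthy controls".

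The protocol's Research Design and Methods limits what controls provide: "Control subjects will complete the screen and baseline visit only". Contact at 12 months is a telephone call about medical changes and life events. The 6- and 12-month visits, which repeat the baseline DXA and HR-pQCT, are headed as being for AN subjects only. The baseline item on MRI and MR spectroscopy restricts the repeat to AN, and the remuneration section pays healthy subjects for a single visit. DXA may be done at screening if it cannot be done at baseline, which moves the one scan and does not add another.

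Two statements sit badly with this schedule. Research Design and Methods first describes controls as having prospective follow-up over 12 months. The SAP's opening paragraph describes measurements every three to six months and lists three groups without saying which groups have repeats.

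For Aim 2B the protocol speaks of improvement "more than estrogen alone to approach that in normal adolescent girls", and the SAP says "When comparing with healthy adolescent girls, we will adjust for multiple comparisons". Neither says whether level or change is compared.

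**The concern.** A rate of accrual within girls needs at least two measurements per girl in each group compared. The controls have one, so a named aim has no analysis that its own data can support. The protocol and SAP carry the same version date (March 29, 2018), so this is not a lag between versions, and no external control slope is named.

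The failure could also go unnoticed. Software that meets two identical columns usually drops one. If the time column is dropped, the term labelled group by time is simply the AN slope tested against zero. A positive result could then be reported as AN girls gaining more than controls, which is the result the SAP expects. If instead the problem is found at analysis, the replacement would be chosen after the data are seen.

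**Working it through.** **Inputs.** From the SAP's Sample Size Determination: intercept variance 0.01056, slope variance 0.001523, covariance −0.001, residual variance 0.000533; 50 girls per AN arm; 20% dropout; slope difference 0.03 g/cm²/year; two-sided 0.05; 80% power. From the protocol: AN scans at 0, 6 and 12 months, controls at 0 only, 36 controls, eligibility age 14 to 22.

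**1. The plan's own figure.** The SAP gives no power for Aim 1C, so the check is on the Aim 1A model that it reuses. The variance of one girl's slope from three scans is 0.001523 + 0.000533/0.5 = 0.002589 (SD 0.0509).
- 50 complete per arm: SE = √(2 × 0.002589/50) = 0.0102, power 84%.
- 40 complete per arm: SE = 0.0114, power 75%.
- 20% lost after month 6: SE = 0.0108, power = Φ(0.03/0.0108 − 1.96) ≈ 79.5%.

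The stated 80% is reproduced, so the model is understood as intended.

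**2. Estimability of Aim 1C.** Rows of the design, in the order intercept, group (AN = 1), time, group × time:
- AN: (1, 1, 0, 0), (1, 1, 0.5, 0.5), (1, 1, 1, 1)
- Control: (1, 0, 0, 0)

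The last two columns are identical, so the rank is 3 of 4. The information on the control slope is exactly zero, and more controls do not change that. Adding a control row at 12 months, (1, 0, 1, 0), gives rank 4.

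**3. What one control scan can support.** Regress the controls' single scans on age, take the expected one-year gain at the AN girls' ages, and subtract it from the observed AN gain. Assume that the AN variances hold in controls, that 40 AN girls complete, and that ages are evenly spread within each range.
- AN slope SE = √(0.002589/40) = 0.00805.
- Control single-scan SD = √(0.01056 + 0.000533) = 0.1053.
- Detectable difference = (1.960 + 0.842) × √(AN SE² + reference SE²).

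With a quadratic in age fitted to 36 controls:

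| Control ages | AN ages | Reference SE | Detectable difference, g/cm²/year |
|---|---|---|---|
| 14–22 | 14–22 | 0.0082–0.0085 | 0.032–0.033 |
| 14–22 | 14–18 | 0.0128–0.0134 | 0.042–0.044 |
| 14–22 | 18–22 | 0.0189–0.0199 | 0.058–0.060 |
| 16–22 | 14–22 | about 0.012 | about 0.040 |
| 14–18 | 14–22 | 0.071–0.075 | about 0.20 |

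Ranges within a row reflect how the even age grid is placed. A straight line in age would give 0.031 in the first row, but the protocol's background says that most bone mass is accrued by 18, so curvature has to be allowed. If AN ages are even over 14 to 22, 1 in 8 girls pass 22 during follow-up and the reference is extrapolated for them.

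**4. A 12-month control scan instead.** Control slope SE = √((0.001523 + 2 × 0.000533)/36) = 0.0085, or 0.0094 with 29 returning. Combined with 0.00805 this is 0.0117 or 0.0124, and the detectable difference is 0.033 or 0.035. The 36 case pairs no control loss with 20% AN loss, so it is the favourable end.

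**The case against.** The strongest objection concerns reach. Aim 1C is a non-randomized, non-primary comparison with no power claim, and both primary endpoints compare one AN arm with the other. That is correct: the trial's main inference does not depend on this point, and Aim 2A needs only one control scan.

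A reader might infer that Aim 2B has the same gap, because it analyses change and then mentions healthy girls. The documents do not support that. The SAP commits only to a multiplicity adjustment for that comparison, and the protocol's wording can be read as a comparison of levels, which one control scan supports. The ambiguity stands; a failed analysis there does not.

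It can also be said that age could serve as the time axis, so that controls of different ages yield a slope. That is a between-girl age gradient, not accrual within girls, and the SAP does not plan it.

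Finally, the precision figures rest on assumptions. That also stands. Eligibility ages are given but the age mix of neither group is, and the control mix matters most. The residual SD around an age curve may be below 0.1053; at an assumed 0.08 the first three rows of the table fall to about 0.029, 0.035 and 0.046. None of this touches the rank result, which needs no assumption. Nor is the SAP's percent-predicted scaling a full precedent for the replacement: it is introduced outside the specific aims and mentions no age adjustment. It shows only that controls' data are already meant to serve as a reference.

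**Conclusion.** The point holds for Aim 1C and should be corrected before analysis. With one scan per control, 0 of 36 controls inform a slope, the design has rank 3 of 4, and the planned contrast cannot be estimated at any sample size. This follows from the visit schedule alone. The protocol's description of 12-month prospective follow-up of controls conflicts with that schedule and must be reconciled with it.

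For Aim 2B the conclusion is narrower: the plan does not say what is compared with healthy girls, and only a comparison of change would be lost. The randomized comparisons and Aim 2A are unaffected.

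The precision of any single-scan replacement is conditional on AN variances holding in controls, 40 AN completers and the age mixes shown. Every quadratic case at the SAP's own variances gives a detectable difference above 0.03 g/cm²/year, the slope difference on which the trial is powered. The SAP states no expected AN–control difference, so adequacy cannot be judged from the documents.

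**What to change.** 1. In SAP Aim 1C, delete the control-slope comparison and the expectation that AN change exceeds control change. Replace them with the change from baseline to 12 months in the AN deficit relative to an age-adjusted reference from the controls' baseline scans. Allow curvature in age. Carry the uncertainty of the reference, for example by bootstrapping controls and AN girls together. Report the estimate with a 95% CI under the multiplicity adjustment already promised. Restate protocol aim C to match, and state that a non-significant AN–control difference will not be read as normalization.
2. In Aim 2B, state that comparisons with healthy girls are of level or percent predicted, not of change. The SAP already plans to "transform both to percent predicted using the data from healthy adolescent girls", which needs one scan.
3. Correct the protocol sentence on prospective follow-up of controls, and state in the SAP's opening paragraph that repeated measures apply to the AN groups only.

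**Cost.** Wording only, with no new visit. The downside should be stated in the SAP: a cross-sectional age gradient is weaker evidence than within-girl accrual, depends on the fitted curve, and is extrapolated for AN girls who pass the controls' upper age.

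**Alternative.** A 12-month control scan is the only way to keep Aim 1C as written. It needs no age curve and its precision does not depend on the age mix, but it adds a visit and a scan for up to 36 healthy girls.
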